4.0 Study Endpoints

*4.1 Describe the primary and secondary **study** endpoints. See links below for discussion of study endpoints and how they may differ from study objectives. These are most common in clinical trials but are sometimes applicable to other types of biomedical research, as well as social, behavioral, or educational research. See link below for a discussion.*

https://docs.google.com/document/d/1Wocz7K7a0hCQJPPO_khh511SQjhGDDGHzcOPRHR5Tw/edit?usp=sharing

Delay discounting: Change in discounting rates will be compared within-subjects between pre intervention and post intervention. In addition, differences in discount rates will be compared between groups (EFT and CET).

Alcoholic Drinks: Change in drinks per day and number of positive breath alcohol samples (BrAC) will be compared within-subjects between pre intervention and post intervention. In addition, differences in drinks per day and number of positive BrAC samples will be compared between groups (EFT and CET).

Alcohol Demand: Change in demand for alcohol will be compared within-subjects between pre intervention and post intervention. In addition, differences in alcohol demand will be compared between groups (EFT and CET).

Alcohol Craving: Change in alcohol craving will be compared within-subjects between pre intervention and post intervention. In addition, differences in alcohol craving will be compared between groups (EFT and CET).

4.2 *Describe any primary or secondary safety endpoints. These should be included for all studies that are greater than minimal risk. (Minimal risk: The probability and magnitude of harm or discomfort anticipated in the research that are not greater in and of themselves than those ordinarily encountered in daily life or during the performance of routine physical or psychological examinations or tests.):*

This study's procedures are not more than minimal risk.

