Primary hypotheses: Our primary measure of temporal window is delay discounting (DD). Our primary measure of alcohol consumption is self-reported drinks per day. Participants are asked to report how many standard drinks they had for the previous 24 hours on each day of the 7 day baseline and 28 day intervention period. Our secondary measure of alcohol consumption is breath alcohol samples from the remote breathalyzer. Participants will provide three breath samples daily for the 7 day baseline and 28 day intervention period. Our primary measures of demand are alpha and Q0. Alpha and Q0 are two derived outcomes from a hypothetical alcohol purchase task. Participants are asked to report the number of standard drinks they might hypothetically purchase at increasing price points. Q0 is a measure of how many drinks a participant might purchase when drinks are free (price = \$0). Alpha is a measure of the participants sensitivity to increasing prices (i.e., how quickly they decide to stop purchasing at higher prices). Our measure of craving is the Alcohol Urges Questionnaire (AUQ). Our measure of neural activity is BOLD response. We hypothesize that baseline BOLD response will be predictive of the efficacy of the intervention. We will model our primary outcome measures using a mixed-effects hierarchical model that includes day, time (pre/post intervention), and intervention group. A random effect will be included for each participant. We will include baseline BOLD response as a fixed-effect covariate in our analysis.

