Cellular phone communication. All participants will either be allowed to use their own personal cell phone for study communications or receive a cell phone with service through a nationwide cell phone service provider. If a participant chooses to use their personal cell phone for study communications and pays for text messages and/or phone calls on a per unit basis, we may reimburse the participant for the cost of those messages and calls made for this study. We have used study-provided cell phones to facilitate study communication previously (Athamneh et al., 2021, [name] et al., 2011).

BACtrack breathalyzer monitoring. The BACtrack breathalyzer (<https://www.bactrack.com>) contains a number of technological advances that make it ideally suited for remote breath samplings of alcohol use. To complete scheduled breathalyzer assessments, participants will log into the Remote Monitoring app on their smartphone, developed by the University of Kentucky. Participants will select to submit a breath sample and participants will simply blow into the device for a few seconds. The breathalyzer will be provided to the participants for the study. Participants will be able to keep their breathalyzer following completion of the study. If the breathalyzer is lost/stolen/damaged, the participant will be able to receive a new breathalyzer from the study team.

All participants will be asked to complete breathalyzer screens 3 times per day for approximately 35 days (approximately 7 days baseline, and approximately 28 days intervention). A period of approximately 28 days of the intervention was chosen to

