We will use a 3T Siemens MAGNETOM Prisma^{fit} scanner (Siemens, Erlangen, Germany) with a 20-channel head/neck coil. T1-weighted images will be acquired at $1 \times 1 \times 1 \text{ mm}^3$ resolution using 3D MPRAGE, FOV = $256 \times 256 \times 176 \text{ mm}^3$, TR/TE/TI = 1950/4.44/950 ms, FA = 12° , phase partial Fourier 7/8, slice partial Fourier 6/8, GRAPPA factor = 4 with 33 reference lines, and bandwidth = 140 Hz/pixel. Functional BOLD data will be acquired using EPI with thirty-three 4 mm interleaved slices with a 10% slice gap, TR/TE = 2000/30 ms, FA = 10° , in-plane resolution of $3.4 \times 3.4 \text{ mm}^2$, anterior-to-posterior phase encoding and a bandwidth = 2442 Hz/pixel. Participants will be instructed to keep their eyes open during the scan and direct their gaze on a white plus (+) sign centered on a black background.

Alcohol Consumption

Changes in drinks per day and the number of positive breath alcohol samples (BrAC) will be compared within subjects between pre-intervention and post-intervention. In

addition, differences in drinks per day and the number of positive BrAC samples will be compared between groups (EFT and CET). A Timeline Follow Back (TLFB⁴⁰) will be conducted during Session 2 (pre-intervention) and Session 6 (1-month follow-up) to assess the number of alcoholic drinks consumed daily for the past 30 days. During the intervention period (from Session 2 to Session 5), participants will report daily the number of alcoholic drinks consumed.

Alcohol Urges Questionnaire (AUQ)

The Alcohol Urges Questionnaire ⁴¹ will be used to assess craving for alcohol. This 8-question measure of drinking urges is scored by summing responses to a 7-point Likert scale. The dependent measure of the summed score will be compared within subjects between pre-intervention and post-intervention. In addition, differences in alcohol craving will be compared between groups (EFT and CET).

Alcohol Use Disorders Identification Test (AUDIT)

The Alcohol Use Disorders Identification Test (AUDIT⁴²) will be used to assess hazardous or harmful alcohol use. AUDIT is a 10-item screening tool that assesses alcohol consumption, drinking behaviors, and alcohol-related problems. Differences in alcohol AUDIT scores will be compared between groups (EFT and CET).

Alcohol Relative Reinforcement Schedule (ARRS)

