Objective 1: *We hypothesize that an intervention involving EFT will increase the temporal window and decrease alcohol valuation (consumption, demand, and craving).*

Our primary measure of alcohol use during the intervention period will be the daily self-reported number of drinks per day and the SOBERLINK breathalyzer screens. We will use generalized linear mixed models to compare the daily number of drinks between the EFT and CET groups. Mixed models is a method suited to the analysis of repeated measurement data. Here, the daily number of drinks will be modeled using a Poisson distribution. In the event the daily number of drinks exhibit over dispersion, other distributions, such as a negative binomial, will be considered. In a similar manner, dichotomous breathalyzer results data (positive or negative) throughout the 5-week field test will be analyzed as a function of intervention assignment, while accounting for time of day (morning, afternoon, evening) and repeated measures from each subject. Intrasubject correlation will be accounted for using an autoregressive correlation structure (AR(1)), since drinking days may be temporally related. In the event the AR(1) correlation structure is not representative of the data, other correlation structures will be considered. All missed assessments, although rare in our experience with similar field studies (approximately 5%), will be included as missing data. In the event of high rates of missing data, we will employ techniques consistent with the intention-to-treat paradigm, such as last observation carried forward methods or worst-case scenario (that all missing data is a positive BrAC measure).

Secondary analyses. In addition to the primary hypotheses listed above, we propose several additional analyses that will more fully characterize the behavior of our research participants and potentially lead to future research questions related to EFT in AUD. To this end, we hypothesize that EFT will result in changes (baseline versus post-intervention) in secondary outcome measures (e.g., Alcohol Withdrawal Symptoms Checklist). All these secondary hypotheses will be analyzed analogous to the primary hypothesis.

Covariate Plan:

We will test for individual differences in outcome measures for the intervention for each of these stratified variables. Therefore, we will include AUDIT score, SES, age, and gender in the analyses testing for an interaction between these variables and the intervention.

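### The BrAC endpoint is a count of positive samples with no denominator, so its pre/post change is confounded with window length (21 versus 84 scheduled samples), and no stated model clearly estimates that change

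*Protocol*

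**What the plan says.** Protocol 4.1 sets the endpoint: "Change in drinks per day and number of positive breath alcohol samples (BrAC) will be compared within-subjects between pre intervention and post intervention". It adds a comparison of the same two quantities between EFT and CET. The SAP, under Data Measures, Alcohol Consumption, uses nearly the same words: "Changes in drinks per day and the number of positive breath alcohol samples (BrAC) will be compared within subjects between pre-intervention and post-intervention". Neither place gives a denominator for the breath result or says which days count as post.

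Protocol 5.2 fixes the sampling: "Participants will provide three breath samples daily for the 7 day baseline and 28 day intervention period". Protocol 8.2 gives the same schedule, with every duration marked as approximate.

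The documents rank the measure differently. Protocol 5.2 states "Our secondary measure of alcohol consumption is breath alcohol samples from the remote breathalyzer", while the SAP under Objective 1 states "Our primary measure of alcohol use during the intervention period will be the daily self-reported number of drinks per day and the SOBERLINK breathalyzer screens".

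Two models bear on the point:

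- Protocol 5.2 describes a mixed model with day, pre/post time and group, but for the primary outcome measures.
- The SAP under Objective 1 models each breath result as positive or negative over the five-week field period. Its terms are assigned group and time of day, with repeated measures and an AR(1) structure. It mentions no pre/post term for this outcome.

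Missed assessments, expected at about 5%, stay missing by default. If missingness is high, the SAP allows last observation carried forward, or counting every missing sample as positive.

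**The concern.** The same sentence pairs a rate (drinks per day) with a count. A rate can be compared across windows of different length, but a count cannot. With four times as many sampling occasions after baseline as during it, a participant whose drinking is unchanged would show a large rise in positives, and one who drinks much less could still show a rise. The remote breathalyzer is the objective field check on self-reported drinking, so a misleading change score here could contradict a real reduction in drinks per day.

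A count also depends on how many samples are submitted. Participants who miss samples or leave early have fewer chances to be positive.

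**Working it through.** **Inputs.** Three samples a day, 7 baseline days and 28 intervention days (Protocol 5.2 and 8.2). About 5% of assessments missed (SAP, Objective 1). The documents give no positivity rate, so 10%, 30% and 50% are assumed. A 20% missed share is also assumed, for contrast with 5%.

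**Step 1: the plan's own total.** 7 + 28 = 35 days, which matches the approximate 35 days in Protocol 8.2.

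**Step 2: scheduled samples.** Baseline 3 × 7 = 21; intervention 3 × 28 = 84; total 105. Ratio 84/21 = 4.0.

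**Step 3: expected count with unchanged positivity p.** Expected count = scheduled samples × p.

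| p (assumed) | Baseline, 21p | Intervention, 84p | Ratio |
|---|---|---|---|
| 10% | 2.1 | 8.4 | 4.0 |
| 30% | 6.3 | 25.2 | 4.0 |
| 50% | 10.5 | 42.0 | 4.0 |

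The factor of four does not depend on p.

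**Step 4: true reductions.** If positivity falls by a share r, the count ratio is 4 × (1 − r). A fall of 50% gives 2.0, so the count still doubles. Equality needs 4 × (1 − r) = 1, so r = 75%.

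**Step 5: between arms.** With unchanged positivity the expected change in each arm is 84p − 21p = 63p (18.9 at 30%). The term is the same in both arms when they share p, so it cancels from the EFT minus CET difference.

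**Step 6: missed samples and dropout, default rule.** At 30% positivity the intervention count is 84 × 0.95 × 0.30 = 23.9 with 5% missed, and 84 × 0.80 × 0.30 = 20.2 with 20% missed. If one arm missed 20% and the other 5%, the count ratio would be 0.80/0.95 = 0.84 with no difference in drinking. A participant who leaves after 14 intervention days has 3 × 14 = 42 scheduled samples, half of 84.

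**Step 7: missed samples, worst-case option.** With missing counted as positive, 30% becomes 0.30 × 0.95 + 0.05 = 33.5% with 5% missed, and 0.30 × 0.80 + 0.20 = 44% with 20% missed. The direction reverses.

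**Step 8: simulation under no change.** The set-up was 76 participants (the completer target in Protocol 14.1), personal positivity drawn from Beta(1.8, 4.2) with mean 0.30, all samples submitted, a paired t-test at 0.05, and 2,000 runs. The test on raw counts rejected in 100% of runs, in the direction of more drinking. The test on proportions rejected in 4.4%.

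**Step 9: is there another stated analysis of the change?** The SAP's breath model has a group term but no period term. As worded, it estimates an average arm difference over the field period, not a change. Protocol 5.2's model has a period term but is stated for primary outcomes, and the same section ranks breath samples as secondary.

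**The case against.** The best defence is that the count is only a label. The endpoint list and the data-measures paragraph specify no test. The one breath-specific analysis works sample by sample, where window length and samples missed at random do not shift the estimate. This stands for the arm comparison. It does not stand for the within-subject change, which both documents promise and which that model, as written, does not estimate. One could argue that the SAP promotes breath samples to primary, so the Protocol's pre/post model applies, but neither document says so.

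It is also fair that post is undefined, so equating it with the 28 days is an inference. Laboratory sessions include breath tests too, but no remote sampling is scheduled after the intervention period. The SAP adds to the uncertainty by describing the intervention period as running from Session 2 to Session 5, which takes in the baseline week.

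Two stronger readings are tempting, and the documents do not support them:

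- **That the fourfold factor biases EFT against CET.** It does not, because the scheduled windows are the same in both arms.
- **That poor compliance must look like less drinking.** This holds for a raw count under the default rule, but the worst-case option pushes the other way. The SAP expects only about 5% missed and plans checks of missingness and attrition by arm. Payment per sample does not depend on the result. No figure in the documents supports a large difference in submission between arms.

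**Conclusion.** The point holds for the within-subject change. As defined in both documents, the breath endpoint would rise fourfold with unchanged positivity, would double under a true halving, and would show no change only after a 75% fall. These ratios hold at any positivity rate. They assume full submission and that post means the roughly 28-day intervention period.

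The randomised comparison is not biased by window length, and the SAP's per-sample model is sound on that score. A raw between-group count would still be sensitive to missed samples and early dropout. The direction depends on which missing-data rule is applied, and the size (0.84 in the example) rests on an assumed difference in submission. With about 65% of eligible participants expected to complete (Protocol 14.1), or 70% retained after baseline (SAP, Participant Retention), unequal exposure between individuals is likely even if the arms are balanced.

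What remains is a mismatch between a count endpoint and a per-sample analysis, plus a promised change that has no sound stated analysis.

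**What to change.** 1. In Protocol 4.1 and the SAP's Alcohol Consumption paragraph, replace the number of positive BrAC samples with the proportion of submitted remote samples that are positive, calculated separately for baseline and intervention.
2. Define the pre window as baseline monitoring (Session 2 to Session 3) and the post window as intervention monitoring (Session 3 to Session 5). Correct the SAP phrase that starts the intervention period at Session 2.
3. Add period and period-by-group terms to the SAP's per-sample binary model. With CET as reference, the period term gives the change in CET, period plus interaction gives the change in EFT, and the interaction gives the difference between them.
4. Tabulate scheduled and submitted samples by arm and period.

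The cost is a few lines of text and one extra table, with no new data. The limitation is that a proportion of submitted samples does not remove bias if participants skip samples when they have been drinking. The SAP's missing-data options and planned missingness checks are therefore still needed, and the worst-case analysis should state that its denominator is scheduled samples.

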5.0 Study Design and Statistical Analysis Plan

5.1 *Describe the basic study design/approach (e.g., qualitative study using five focus groups of first year students to describe assimilation into the university community; randomized controlled trial of a behavioral change intervention to increase dietary intake of whole grains; pre- post-test evaluation of new pedagogical techniques to improve adult literacy):*

Participants will be randomly assigned to experimental or control groups, stratified by demographic characteristics (e.g., drinks per day and baseline delay discounting rates). Based on our 8 years of experience recruiting this population, we expect approximately 66% retention among eligible participants. Therefore, we will enroll approximately 200 participants in order to conclude with 76 completers. We plan to enroll more than our average attrition rate because of the increased screening procedures and the time demands of the study. Randomization will be stratified on demographic characteristics (e.g., drinks per day and baseline delay discounting rate). As a result, any differences observed in our primary hypotheses will not be confounded by these variables.

EFT group participants will be asked to think about and describe the most positive event that could realistically happen at a number of delays in the future (e.g., 1 day, 2 weeks, 1 month, 1 year, 5 years, 25 years). In contrast, participants randomized to the CET condition, will be asked to think about and describe the most positive event that occurred at a number of time points from the recent past (e.g., last night from 7pm-10pm, yesterday between 4pm-7pm, yesterday between 1pm-4pm, yesterday from 10am-12pm, yesterday between 7am-10am, the night before last between 7pm-10pm, and evening before last between 4pm-7pm).

5.2 *Describe corresponding data analysis plan/approach (e.g., content analysis of focus group transcripts; descriptive analysis followed by linear regression modeling; nonparametric analysis of pre- and post-test measures):*

Primary hypotheses: Our primary measure of temporal window is delay discounting (DD). Our primary measure of alcohol consumption is self-reported drinks per day. Participants are asked to report how many standard drinks they had for the previous 24 hours on each day of the 7 day baseline and 28 day intervention period. Our secondary measure of alcohol consumption is breath alcohol samples from the remote breathalyzer. Participants will provide three breath samples daily for the 7 day baseline and 28 day intervention period. Our primary measures of demand are alpha and Q0. Alpha and Q0 are two derived outcomes from a hypothetical alcohol purchase task. Participants are asked to report the number of standard drinks they might hypothetically purchase at increasing price points. Q0 is a measure of how many drinks a participant might purchase when drinks are free (price = \$0). Alpha is a measure of the participants sensitivity to increasing prices (i.e., how quickly they decide to stop purchasing at higher prices). Our measure of craving is the Alcohol Urges Questionnaire (AUQ). Our measure of neural activity is BOLD response. We hypothesize that baseline BOLD response will be predictive of the efficacy of the intervention. We will model our primary outcome measures using a mixed-effects hierarchical model that includes day, time (pre/post intervention), and intervention group. A random effect will be included for each participant. We will include baseline BOLD response as a fixed-effect covariate in our analysis.

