counterbalanced to either the active or control group based on alcohol use (e.g., average drinks per day) and their baseline delay discounting rate. Both groups will be exposed to the same procedures. That is, participants in both groups will generate positive cues at either future timepoints (active, Episodic Future Thinking, EFT) or recent timepoints (control, Control Episodic Thinking, CET). Following this Session 3, participants will begin the first intervention period (Monitoring Part 1). The intervention period will last approximately 14 consecutive days, with three breathalyzer screens per day. During this 14-day period, participants will also self-report their previous-day alcohol use daily remotely and their alcohol withdrawal symptoms per day. Following Monitoring Part 1, participants will return to the laboratory for Session 4, where they will generate new cues and complete assessments. Following Session 4, participants will begin the second intervention period (Monitoring Part 2). The intervention period will last approximately 14 days, with three breathalyzer screens per day. During this second 14-day period, participants will self-report their previous-day alcohol use remotely. Session 5 will be conducted in the laboratory after the conclusion of Monitoring Part 2. Participants will also complete Session 6 (1-month follow-up) one month after the conclusion of the intervention. Participants may be provided a cell phone (if necessary) at the beginning of the study and a BACtrack breathalyzer at the beginning of the baseline period.

Participants may receive a \$100 study completion bonus at the end of the study provided they complete all six sessions (and return the cell phone if applicable). Please note: if participants are unable to complete the entire 28-day intervention period, post-intervention data will be collected regardless of the number of intervention days completed.

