Exclusion criteria include: (1) meeting moderate to severe DSM-5 criteria for substance-use disorders other than alcohol, nicotine, or marijuana, (2) having a current diagnosis of any psychotic disorder, (3) having a history of seizure disorders or traumatic brain injury, (4) having any contraindication for participation in the fMRI session, or (5) reporting current pregnancy or lactation.

Recruitment

Participants will be recruited from the community via posted flyers, word of mouth referrals, and electronic advertisements (e.g., Craigslist, Facebook). Participants may contact the lab directly via email, Facebook, phone, walk-in, face-to-face at tabling events, or completing the online pre-screening questionnaire. Participants will also be contacted directly if they have given prior permission (through previous informed consent form) or by completion of a confidential pre-screening questionnaire.

We have developed and are currently using a separate pre-screening protocol, which occurs prior to enrolling participants into our intervention protocols, to effectively decrease attrition in our studies by ensuring that participants meet most inclusion/exclusion criteria (e.g., MRI scanner eligibility) prior to enrolling into the randomized study. Given that this separate screening protocol is used for all currently on-going studies in the lab, we cannot accurately estimate the total number of potential participants we expect to screen. However, as described above, we expect enrolling 170 participants to complete 54. We plan to enroll more than our average attrition rate because of the increased screening procedures and the time demands of the study. Additionally, the first few participants enrolled into the study may be pilots.

Participant Retention

We will evaluate continuation in our study after a baseline period of drinking has been completed. We expect to retain 75% of our participants at this time point. Specifically, 75% of our participants will present with at least 4 out of 7 drinking days, and at least 4 days with 4 or more drinks or an average higher than 4 drinks per day on drinking days.

Once participants reach this study phase , we expect a 70% retention for the rest of the study.

Randomization

Participants will be randomly assigned to experimental or control groups, balanced by number of drinks per day (square root transformed) and baseline DD rates.

Sample size

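### Allocation is balanced on baseline drinks per day and baseline discounting, but no stated model adjusts for either, and the SAP's Covariate Plan names four other variables as the stratified ones

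*Protocol*

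**What the plan says.** **Allocation.** Protocol 5.1: "Randomization will be stratified on demographic characteristics (e.g., drinks per day and baseline delay discounting rate". From this it infers that "any differences observed in our primary hypotheses will not be confounded by these variables". Protocol 8.2 has participants "counterbalanced to either the active or control group based on alcohol use (e.g., average drinks per day) and their baseline delay discounting rate". The SAP, under Randomization, has the groups "balanced by number of drinks per day (square root transformed) and baseline DD rates".

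**Models.** For drinks, SAP Objective 1 says "We will use generalized linear mixed models to compare the daily number of drinks between the EFT and CET groups", with no baseline covariate stated. Breathalyzer results are analysed "as a function of intervention assignment, while accounting for time of day (morning, afternoon, evening) and repeated measures from each subject". For DD, the SAP compares ln(k) between the groups. The model in Protocol 5.2 has day, pre/post period and group, a participant random effect, and baseline BOLD response as its only named covariate.

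**Covariate Plan (SAP).** "We will test for individual differences in outcome measures for the intervention for each of these stratified variables". The next sentence supplies the list: "we will include AUDIT score, SES, age, and gender in the analyses testing for an interaction between these variables and the intervention".

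**Sample size.** Protocol 14.1 assumes an ANCOVA with the baseline measure as a covariate. The SAP assumes a group-by-time interaction in a repeated-measures ANOVA.

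**The concern.** A factor used to balance the arms normally belongs in the analysis. Balancing makes the estimated treatment difference more precise. If the factor is then left out, its variation stays in the error term, so the standard error is too large. The test rejects less often than its nominal level and power is lost. A trial needing only 52 (SAP) or 76 (protocol) completers has little to spare.

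Two matters of wording compound this. The Covariate Plan's reference to stratified variables matches nothing in the SAP's Randomization section, so an analyst could believe the allocation factors are covered when they are not. Its four variables also enter as treatment interactions, which address effect modification and not prognostic adjustment. And the protocol's assurance rests on balance at allocation, whereas both documents size the trial on completers.

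**Working it through.** **1. Text check.**

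| Place | Baseline drinks per day | Baseline DD | AUDIT, SES, age, gender |
|---|---|---|---|
| Protocol 5.1 and 8.2, SAP Randomization | balancing factor | balancing factor | not named |
| Protocol 5.2 model | not a covariate | not a covariate | not named |
| SAP drinks and breathalyzer models | not a covariate | not a covariate | not named |
| SAP Covariate Plan | not named | not named | called stratified; entered as interactions |

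**2. The plan's own figures.** SAP: f = 0.25, correlation 0.5, 2 measurements, alpha 0.01, power 80%. The noncentrality is f² × N × m/(1 − ρ) = 0.0625 × 52 × 2/0.5 = 13. With 1 and 50 degrees of freedom this gives 81.8% power, and 52 is the smallest even N reaching 80%, so it reproduces. The protocol's 76 does not follow from its stated ANCOVA inputs: 2(2.576 + 1.645)²/0.5² × (1 − 0.70218²) = 72.2, so 73 per group and 146 in all. That is a separate matter. Here 76 is only the planned number of completers.

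**3. Cost of leaving out a balanced baseline.** Assumptions: normal outcome with SD 1, equal arms, close balance, two-sided 0.05, difference of 0.5 SD (2f). The baseline-outcome correlation r is 0.5 (SAP) or 0.7 (protocol, printed as 0.70218).

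- True standard error under close balance: √(4(1 − r²)/N).
- A change-score test uses a standard error too large by √(2/(1 + r)): 1.155 at r = 0.5, 1.085 at r = 0.7. Its actual type I error is P(|Z| > 1.96 × that factor), about 2.4% and 3.4%.
- A post-only test uses one too large by 1/√(1 − r²): 1.155 and 1.400. Its actual type I error is about 2.4% and 0.6%.

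Worked case, N = 52, r = 0.5: standard error √(4 × 0.75/52) = 0.240, so the effect is 0.5/0.240 = 2.08 standard errors. The change-score test needs 2.009 × 1.155 = 2.32. Power is about P(Z > 2.32 − 2.08) = 41%. The adjusted test (noncentral t, 49 degrees of freedom) has 53%.

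| N | r | Post-only | Change score | Adjusted |
|---|---|---|---|---|
| 52 | 0.5 | 41% | 41% | 53% |
| 76 | 0.5 | 59% | 59% | 70% |
| 52 | 0.7 | 39% | 64% | 70% |
| 76 | 0.7 | 60% | 81% | 85% |

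Simulation (sorted blocks of four on baseline) agrees to within about one percentage point.

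**4. Loss after allocation.** The SAP expects 70% retention after the baseline period, a 30% loss. Protocol 14.1 expects about 65% of those randomised to finish, a 35% loss.

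**The case against.** **Baseline values are not wholly unused.** Protocol 5.2 has a pre/post term, both documents describe within-subject change, the breathalyzer analysis spans all five weeks, and the SAP is sized on a group-by-time test. An outcome's own baseline can thus enter as a repeated measure. This stands. A reader might infer that adjustment lifts power from 39% to 70% (N = 52, r = 0.7), but that applies only to a post-only comparison. The SAP's drinks sentence leaves open whether baseline days are included; most of the text points to pre/post analysis. At r = 0.5 the change score gives no relief.

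**The illustration is favourable to the point.** Participants are randomised one at a time and no algorithm is given, so sorted blocks are a best case. With sequential blocks within a median split, post-only type I error is about 3% (r = 0.5) or 2% (r = 0.7). Drinks will be modelled as counts, not as normal data. The 0.5 SD effect is also an assumption: in the SAP's interaction formula, f = 0.25 is a difference in change of 4f = 1.0 SD. At 1.0 SD, with N = 52 and r = 0.5, the same formulas give 97% against 98%. These limits stand.

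**The correlations are for an outcome's own baseline.** Neither document says how strongly baseline DD predicts drinking, demand or craving, or baseline drinking predicts DD. For those pairings the gain is unknown.

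**Dropout is not ignored.** The SAP checks attrition by arm and by assessment values at each stage, Protocol 8.2 collects post-intervention data however many intervention days were completed, and a mixed model need not be confined to completers. But the SAP's checks document bias without adjusting for it, and Protocol 16.3 takes withdrawn participants out of the whole study.

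**Protocol 5.1 gives its factors as examples**, so others are possible there. The SAP names exactly two.

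**Conclusion.** The point holds. Neither balancing factor is a covariate in any stated model. The Covariate Plan mislabels four other variables, and the baseline adjustment assumed in Protocol 14.1 was not carried into Protocol 5.2 or the SAP.

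The consequence is a conservative test and some lost power: about 11 to 13 points at r = 0.5 and 4 to 6 points at r = 0.7 against a change-score test, given a 0.5 SD effect and close balance, and less with a larger effect or looser balance.

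Two stronger readings are not supported. One is that omitting the factors confounds the comparison: under sound randomisation it does not. The other is that balance is destroyed by dropout: the documents show only that it is not guaranteed after a 30% to 35% loss. That is enough to make the protocol's assurance too strong. This is worth correcting before the groups are compared; it does not invalidate the trial.

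**What to change.** 1. Model intervention-period outcomes as the response, with square-root baseline drinks per day, baseline ln(k) and the outcome's own baseline as fixed covariates.
2. If baseline observations stay in the model as responses, do not also enter their mean as a covariate, since that uses the same data on both sides. Use a constrained-baseline model (common baseline mean in both arms) and add only the other balancing factor: ln(k) in the drinks model, square-root drinks in the DD model. For demand and craving, neither factor is the outcome's own baseline, so both are added.
3. State in the SAP whether the baseline days are responses in the drinks model.
4. Reword the Covariate Plan so that AUDIT, SES, age and gender are exploratory effect modifiers, not stratification variables.
5. Soften the sentence in Protocol 5.1: balance is sought at randomisation, and residual imbalance is handled by adjustment.

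Cost: SAP and protocol text, plus one modelling decision (items 1 to 3). Both balancing variables must already exist before allocation, so no new data are needed. Settling this before the group comparison also avoids a post hoc choice of covariates.
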